### 2.2 TRIAL OBJECTIVES

This randomized, open label Phase III trial will be performed in patients with squamous cell carcinoma of the lung.

#### 2.2.1 Primary Objective

The primary objective of the trial is to compare the efficacy of afatinib with erlotinib as second-line treatment for this group of patients, as measured by PFS.

#### 2.2.2 Secondary Objectives

The key secondary trial objective is to compare the OS in both treatment groups.

Other secondary objectives are to compare the ORR, DCR and tumour shrinkage of afatinib with erlotinib, and the assessment of HRQoL and safety in both treatment groups.

Study endpoints are provided in Sections [5.1](#), [5.2](#), and [5.3](#).

## 2.3 BENEFIT - RISK ASSESSMENT

Treatment options for patients with advanced squamous cell carcinoma of the lung are limited following first-line chemotherapy, with most patients recurring and eventually succumbing to their disease. For patients eligible to tolerate, chemotherapy has been an option and docetaxel is indicated in the second-line setting for patients with advanced NSCLC with associated chemotherapy related morbidity. Afatinib is an irreversible EGFR inhibitor with a favourable risk benefit ratio that is currently in Phase III clinical trials in lung cancer, breast cancer and squamous cancer of head and neck (SCCHN). The clinical experience of afatinib includes over 2000 patients. Afatinib is relatively well tolerated, with most common adverse events being diarrhoea, rash and stomatitis as expected for this class of agents.

Although rare, a potential for drug-induced liver injury (DILI) is under constant surveillance by sponsors and regulators. Therefore, this study requires timely detection, evaluation, and follow-up of laboratory alterations of selected liver laboratory parameters to ensure patients' safety.

Afatinib has shown evidence of clinical activity in patients with squamous cancer of the head and neck in a randomized clinical Phase II trial and early evidence of clinical activity in patients with squamous carcinoma of the lung in ongoing clinical trials ([P10-12525](#), [P10-12526](#)). This study will have an interim futility analysis planned for the first 176 patients and is outlined in [Section 7.3.4](#). In addition a Steering Committee providing study oversight and a Data Monitoring Committee (DMC) is planned. See [Section 3.1.1](#) for a detailed description of the procedures of these committees.

The large unmet medical need of this patient population combined with the above and the planned interim futility analysis supports the validity of this study.

### 3. DESCRIPTION OF DESIGN AND TRIAL POPULATION

#### 3.1 OVERALL TRIAL DESIGN AND PLAN

This randomized, open-label Phase III trial is designed to compare the efficacy of afatinib with erlotinib for the second-line treatment of patients with advanced NSCLC of squamous or predominantly squamous histology. The primary endpoint of the trial will be progression-free survival.

Eligible patients will be randomized in a 1:1 fashion to receive either afatinib or erlotinib. Patients will receive continuous daily dosing of study drug assigned until disease progression, unacceptable adverse events or other reason necessitating withdrawal (see [Appendix 10.1](#) and Sections [4.1.4](#) and [3.3.4](#)). Study drug dose will be modified as in Section 4.1.4 for the management of adverse treatment effects. The starting dose of afatinib will be 40 mg daily oral and erlotinib will be 150 mg daily oral. For patients adequately tolerating therapy the dose of afatinib will be further titrated to 50 mg daily oral at the end of 4 weeks.

Patients will have tumour assessments at the intervals specified in the [flow chart](#) for assessment of response. Tumour assessment must continue for patients who discontinue study drug due adverse events until the patient experiences disease progression or starts other anti-cancer treatment. Tumour response and progression will be assessed according to RECIST 1.1 ([R09-0262](#)) and assessment at the investigator site will be sufficient for decisions on continuation of treatment (Appendix 10.1). An independent analysis of response will also be performed by a Central Imaging Unit (see [Section 5.1.2.1.1](#)); however this will not be used to make treatment decisions. After approval of Protocol Version 3.0, the central imaging review of tumour response will be discontinued.

All patients will also have regular evaluations for assessment of safety parameters as detailed in the flow chart.

An End of Treatment (EOT) evaluation is to be completed when a patient permanently discontinues study drug, either for disease progression or any reason listed in [Section 3.3.4](#). The assessments required are listed in the flow chart. Patients who discontinue study drug due to toxicity will continue to have tumour assessments according to the Flow Chart until disease progression.

A Follow-up evaluation will be completed 28 (+7) days after permanent discontinuation of study drug. Refer to the flow chart and diagram below for details. This visit will be defined as the last visit for this trial.

Patients will subsequently be monitored for vital status in the Observation Period of this protocol. Once Protocol Version 3.0 is final (and where required locally, approvals are obtained by the site as per [Section 8.1](#)), the collection of vital status data will no longer be required.

The trial is considered completed when:

**Proprietary confidential information.**

© 2016 Boehringer Ingelheim International GmbH or one or more of its affiliated companies. All rights reserved.

[figure not shown]
This document may not - in full or in part - be passed on, reproduced, published or otherwise used without prior written permission.

1.) The PFS and OS events required for analysis in [Section 7.3](#) have occurred.

AND

2.) All patients have discontinued trial medication, as explained in [Section 3.3.4](#).

The diagram below depicts the stages of a patient’s participation in this protocol.

\*For patients who discontinue study drug due to Adverse Event

### 3.1.1 Administrative structure of the trial

The coordinating investigators are oncologists with experience with this type of trial and investigations. The coordinating investigators have been designated by BI and will sign the clinical trial report.

The trial will be performed by investigators specialised in oncology.

**Proprietary confidential information.**

© 2016 **Boehringer Ingelheim International GmbH** or one or more of its affiliated companies. All rights reserved.

This document may not - in full or in part - be passed on, reproduced, published or otherwise used without prior written permission.

A steering committee including the coordinating investigators, experienced investigators and BI representatives will monitor the trial on a regular basis (all operational aspects, recruitment issues, data quality, etc.). A steering committee charter will be prepared specifying the objectives of the committee.

A data monitoring committee (DMC) will be formed consisting of three experienced and independent members, including two clinicians and one biostatistician who, collectively, have expertise in the management of patients with lung cancer and in the conduct and monitoring of randomised clinical trials.

The DMC will meet regularly and their responsibility is to continuously assess the trial data to ensure overall safety in the treated patients, monitor the quality and provide BI and the trial steering committee with advice about the conduct of the trial and the integrity of the data. The DMC will oversee the interim analysis planned in the study. Details of the DMC responsibilities will be described in the DMC charter.

Inclusion of patients in the trial will continue during the scheduled meetings of the DMC. Decisions on trial termination, amendment or cessation of patient recruitment, based on safety or outcome findings will be made after recommendations from the DMC have been assessed by the sponsor.

, a Contract Research Organization (CRO), will be responsible for DMC management and oversight. will also coordinate and provide medical writing support for the DMC charter. Clinical Trial Master File (CTMF) contents relating to DMC conduct will be maintained at through the course of the study, and will be transferred to the BI CTMF at the end of the trial.

On-site monitoring will be performed by BI or a CRO appointed by BI.

BI will appoint CROs and independent service providers for special services such as central independent review of CT scans and MR images, central laboratory services, electronic collection of QoL questionnaires, and Interactive Voice/Web Response System (IXRS) for randomisation and trial medication logistics.

All trial relevant documentation will be stored in the clinical trial master file (CTMF) at BI, with the exception of DMC correspondence as explained above. In addition each site will have an Investigator Site File (ISF) containing all trial documents relevant for the site.

### **3.2 DISCUSSION OF TRIAL DESIGN, INCLUDING THE CHOICE OF CONTROL GROUPS**

This study will be a head-to-head comparison of a reversible first-generation TKI (erlotinib) to an irreversible second-generation TKI (afatinib) as second-line treatment in patients with advanced squamous NSCLC. These patients have a limited life expectancy after disease progression following first-line therapy. This study will evaluate PFS as a primary endpoint; however, the study has adequate statistical power to meet the key secondary endpoint of increased OS in the patients receiving afatinib.

**Proprietary confidential information.**

© 2016 Boehringer Ingelheim International GmbH or one or more of its affiliated companies. All rights reserved.

This document may not - in full or in part - be passed on, reproduced, published or otherwise used without prior written permission.

The unique management of adverse events for afatinib and the comparator, which includes temporary and permanent discontinuation of study drug, presents significant challenges to effectively managing this trial while monitoring patient safety if the patient treatment assignment were blinded to the trial team. Additionally, a double-blinded trial would require either over-encapsulation and subsequent equivalency testing be completed for two distinct packaging schema of the comparator (i.e. bottles in the US and PVC blister-packaging in the rest of world). Therefore, this study will be conducted in an open-label fashion with ICH E9 recommendations to minimize potential bias incorporated ([R08-2251](#)).

Steps to minimize potential bias, especially in the assessment of the primary objective, are in place for this study. These include the use of a central randomization method, to eliminate the potential that an investigator's decision to enroll the next study patient be influenced by knowing the next treatment assignment. The PFS primary endpoint will have an independent radiology review in which the assessors will be blinded. Potential bias of the sponsor management of the trial will be minimized by not allowing the trial team access to aggregate data analysis by assigned treatment groups during the conduct of the study up to formal disclosure of PFS and/or OS results to the trial team (see [Section 4.1.5.1](#)). Any data reviews will present patients in Dummy treatment groups, and all options to complete reviews by aggregate treatment group (i.e. by use of JReview data review tool) will be disabled to all trial team members. The treatment group assignment will be known on a per-patient basis in the eCRF.

Several studies enrolling all NSCLC histologies have been completed with first-generation TKIs. Details of these have been discussed in Sections [1](#) and [2](#).

Initial activity of afatinib in squamous cell carcinoma including NSCLC has been assessed in several trials as described in Sections [1](#) & [2](#).

It is considered that a difference of four weeks improvement in PFS for afatinib compared to the approved treatment (erlotinib) is clinically meaningful in this tough to treat patient population that has limited alternatives for treatment.

### **3.3 SELECTION OF TRIAL POPULATION**

Approximately 800 patients will be randomized at approximately 200 study sites globally. The study will be conducted in approximately 24 countries. The rate of randomization will vary by study site, but is expected to be approximately 2-15 patients per site.

A log of all patients included into the study (i.e. having given informed consent) will be maintained in the ISF at the investigational site irrespective of whether they have been randomized into the trial or not.

#### **3.3.1 Main diagnosis for study entry**

This study will enroll patients with a diagnosis of advanced NSCLC squamous cell histology; who have disease progression after completion of at least 4 cycles of platinum-based doublet

**Proprietary confidential information.**

© 2016 **Boehringer Ingelheim International GmbH or one or more of its affiliated companies. All rights reserved.**

This document may not - in full or in part - be passed on, reproduced, published or otherwise used without prior written permission.

chemotherapy treatment in the 1st line setting of advanced disease; and who are eligible to receive 2nd-line therapy.

*NOTE:* All staging criteria listed below are based on AJCC Staging for NSCLC 7th Edition ([R11-1417](#)).

### 3.3.2 Inclusion criteria

1. Diagnosis of advanced stage NSCLC considered to be squamous histology, including mixed histology, in the opinion of the investigator.
  2. Completion of at least 4 cycles of platinum-based doublet chemotherapy, with or without additional [non-EGFR] targeted agents, as 1st line treatment of Stage IIIB/IV NSCLC. *Note* the below scenarios are also considered to meet this requirement:
    - a. Patients relapsing within 6 months of completing adjuvant/neo-adjuvant/curative -intent chemotherapy/chemoradiotherapy (*Note:* these patients are still required to have had the equivalent of 4 cycles of platinum-based doublet chemotherapy except in setting noted below).
- OR
- b. Patients intending to receive four cycles of platinum-based doublet chemotherapy but due to toxicity, and not PD, discontinue just the platinum agent after at least two cycles of platinum doublet had been administered.
  3. Eligible to receive 2nd line therapy in the opinion of the investigator. Patients who received non-EGFR based therapy for maintenance are eligible.
  4. Measurable disease according to RECIST 1.1 ([R09-0262](#)). Refer to [Appendix 10.1](#).
  5. Eastern Cooperative Oncology Group (ECOG) score of 0 or 1 ([R01-0787](#)). Refer to [Appendix 10.2](#).
  6. Availability of tumour tissue material for correlative studies (refer to [Section 5.6](#)). Archived tumour tissue is acceptable.
  7. Adequate organ function, defined as all of the following:
    - a. LVEF >50% or within institution normal values.
    - b. Absolute neutrophil count (ANC) > 1500 / mm^3. (ANC >1000/mm^3 may be considered in special circumstances such as benign cyclical neutropenia as judged by the investigator and in discussion with the sponsor).
    - c. Platelet count >75,000 / mm^3.
    - d. Estimated creatinine clearance > 45ml / min. Refer to [Appendix 10.3](#).

**Proprietary confidential information.**

- e. Total bilirubin < 1.5 times institutional ULN (Patients with Gilbert's Syndrome total bilirubin must be <4 times institutional ULN).
  - f. Aspartate amino transferase (AST) or alanine amino transferase (ALT) < three times the institutional upper limit of normal (ULN) (if related to liver metastases < five times institutional ULN).
8. Recovered from any previous therapy related toxicity to  $\leq$ CTCAE Grade 1 at study entry (except for stable sensory neuropathy  $\leq$ CTCAE Grade 2 and alopecia).
  9. Ability to take oral medication in the opinion of the investigator.
  10. Age  $\geq$  18 years.
  11. Written informed consent that is consistent with ICH-GCP guidelines.

### 3.3.3 Exclusion criteria

1. Prior treatment with EGFR directed small molecules or antibodies.
2. Curative intent chemoradiotherapy as the only treatment for stage IIIB NSCLC unless relapse occurs within 6 months of completion of treatment, and in the opinion of the investigator the patient has received an equivalent of 4 cycles of platinum-based doublet therapy.
3. Radiotherapy within 4 weeks prior to randomization, except as follows:
  - a. Palliative radiation to target organs other than chest may be allowed up to 2 weeks prior to randomization, and
  - b. Single dose palliative treatment for symptomatic metastasis outside above allowance to be discussed with sponsor prior to enrolling.
4. Active brain metastases (stable for <4 weeks, symptomatic, or leptomeningeal disease). Dexamethasone therapy will be allowed if administered as a stable dose for at least 4 weeks before randomization.
5. Any other current malignancy or malignancy diagnosed within the past three (3) years (other than basal-cell carcinoma of the skin, in situ cervical cancer, in situ prostate cancer).
6. Known pre-existing interstitial lung disease.
7. Significant or recent acute gastrointestinal disorders with diarrhoea as a major symptom e.g. Crohn's disease, malabsorption or CTC grade  $\geq$ 2 diarrhoea of any aetiology, based on investigator assessment.

**Proprietary confidential information.**

© 2016 Boehringer Ingelheim International GmbH or one or more of its affiliated companies. All rights reserved.

This document may not - in full or in part - be passed on, reproduced, published or otherwise used without prior written permission.

8. History or presence of clinically relevant cardiovascular abnormalities such as uncontrolled hypertension, congestive heart failure NYHA classification of 3 (Refer to [Appendix 10.4](#)), unstable angina or poorly controlled arrhythmia as determined by the investigator. Myocardial infarction within 6 months prior to randomisation.
9. Any other concomitant serious illness or organ system dysfunction which in the opinion of the investigator would either compromise patient safety or interfere with the evaluation of the safety of the test drug.
10. Women of child-bearing potential and men who are able to father a child, unwilling to be abstinent or use adequate contraception prior to study entry, for the duration of study participation and for at least 2 months after treatment has ended. Adequate methods of contraception and Women of Child-Bearing Potential are discussed in [Section 4.2.2.3](#).
11. Female patients of childbearing potential (see Section 4.2.2.3) who are nursing or are pregnant.
12. Patients unable to comply with the protocol in the opinion of the investigator.
13. Active hepatitis B infection (defined as presence of Hep B DNA), active hepatitis C infection (defined as presence of Hep C RNA) and/or known HIV carrier.
14. Known or suspected active drug or alcohol abuse in the opinion of the investigator.
15. Requirement for treatment with any of the prohibited concomitant medications listed in [Section 4.2.2](#).
16. Any contraindications for therapy with afatinib or erlotinib.
17. Known hypersensitivity to erlotinib, afatinib or the excipients of any of the trial drugs.
18. Major surgery within 4 weeks of starting study treatment.
19. Prior participation in an afatinib clinical study, even if not assigned to afatinib.
20. Use of any investigational drug within 4 weeks of randomisation (unless a longer time period is required by local regulations or by the guidelines for the investigational product).
21. Patients without Progressive disease.

### 3.3.4 Removal of patients from therapy or assessments

#### 3.3.4.1 Removal of individual patients

The Investigator or subject themselves may stop study treatment at any time for safety or due to patient personal reasons.

If a patient is entered in violation of inclusion/exclusion criteria, the sponsor will determine the medical risk/benefit on a case-by-case basis and can require such a patient be discontinued from the study treatment.

A patient is to discontinue study medication if the patient:

1. Withdraws consent to further study medication.
2. Has radiologically documented progressive disease ([Section 5.1.2](#)).
3. Becomes pregnant ([Section 5.2.2.2](#)).
4. Is diagnosed with ILD.
5. Has the need for study drug discontinuation due to AEs or for further dose reductions considered necessary but not allowed according to the protocol ([Section 4.1.4](#)).

The sponsor may remove patients from the study after completion of the primary efficacy analysis if the patient has access to study treatment via options included but not limited to an alternative clinical trial, marketed product, an expanded-access program, named patient use program, compassionate use protocol or other means based on local regulation. This may mean a change in packaging and labelling. The cost of any ongoing supply of study medication (afatinib or erlotinib) will be incurred by the sponsor until disease progression occurs. If a patient is removed from the study treatment, an end of treatment and a follow up visit 28 days later will be performed to ensure all adverse events are followed up and then the patient will be considered to have completed the trial.

Patients who withdraw from the trial after randomisation will not be replaced.

##### 3.3.4.1.1 Patient discontinuation of study participation

A patient who has discontinued study drug for any of the reasons listed above except reason 5 (i.e. study drug toxicity), will complete a FUP visit and then continue in the Observation Period of the study for vital status and anti-cancer treatment monitoring. Patients who discontinue study drug due to any reasons other than 2 or 3 above will continue to have tumour assessments until disease progression or start of new anti-cancer therapy, following the same schedule Observation Period assessments will be completed as indicated in the [Flow Chart](#). Once Protocol Version 3.0 is final (and where required locally, approvals are obtained by the site as per [Section 8.1](#)), the collection of vital status data will be ceased.

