## FLOW CHART

Visit	Screening	Course 1		Course 2 and subsequent courses*	End of treatment **	Follow-up	Observation Period
Visit Abbreviation	SCR	C1V1	C1V2	CxV1 a	EOT	FUP	OPy b
Day	Up to 28 days before treatment	Day 1 ***	Day 8 (± 2 days)	Day 1 of each course (- 3 to +2 days) ****	0-7 days after permanent discontinuation of study drug	28 Days after discontinuation of study drug (+ 7 days)	Every 28 Days (± 7 days) after FUP
Informed consent	X						
Tumour sample shipment 		X					
Demographics	X						
Medical history	X						
Complete Physical exam 	X				X		
Clinical Assessment 		X	X	X		X	
Vital signs	X	X	X	X	X	X	
Performance status	X	X		X	X	X	
ECG (as indicated) 	X		X	X 	X		
Safety laboratory tests 	X	X		X	X	X	
Pregnancy Test	X	X			X		
ECHO or MUGA 	X			X 	X 		
Review of in-/exclusion criteria	X	X					
Randomization		X					
Collection of blood for Biomarker analysis 		X		X	X		
Patient-reported outcomes 		X		X 	X	X	
Adverse event evaluation 		X-----X					
Concomitant therapy	X	X-----X					
Tumour assessments 	X	Tumour assessments are completed at weeks 8, 12, 16, and every 8 weeks thereafter. After approval of protocol version 3, assessments to be performed every 18 weeks unless clinically indicated.					
Treatment Adherence Check 			X	X	X		
Dispense Trial Drug		X		X			
Termination of trial medication					X		
IXRS	X	X		X	X		
Collection of Vital Status 							X

Proprietary confidential information.

© 2016 Boehringer Ingelheim International GmbH or one or more of its affiliated companies. All rights reserved.

This document may not - in full or in part - be passed on, reproduced, published or otherwise used without prior written permission.

\* All courses are 4 weeks in duration (28 days). Patients may continue on treatment for unlimited courses, until the criteria for stopping medication are met (see [Section 3.3.4.1](#)).

\*\* If the decision to permanently discontinue study drug is taken during a scheduled visit, the EOT visit should be performed instead of the scheduled visit.

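### Protocol Section 3.3.4.1.1 leaves reason-5 patients (adverse events, or dose reductions needed but not allowed) out of the 28-day follow-up visit that the rest of the protocol requires without exception

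*Protocol*

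**What the plan says.** Protocol Section 3.3.4.1 lists five reasons for stopping study drug: withdrawn consent to medication, radiological progression, pregnancy, interstitial lung disease (ILD), and a fifth, "Has the need for study drug discontinuation due to AEs or for further dose reductions considered necessary but not allowed according to the protocol".

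Section 3.3.4.1.1 then says what follows. Its first sentence says that anyone who "discontinued study drug for any of the reasons listed above except reason 5 (i.e. study drug toxicity), will complete a FUP visit"; the Observation Period, for vital status and anti-cancer treatment, comes next. Its second sentence concerns imaging: "Patients who discontinue study drug due to any reasons other than 2 or 3 above will continue to have tumour assessments until disease progression" or new therapy. That sentence then runs on without punctuation: "following the same schedule Observation Period assessments will be completed as indicated in the" flow chart. It does not say which patients this last clause covers.

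Other places set the same two steps without any exception by reason:

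- Section 3.1: "A Follow-up evaluation will be completed 28 (+7) days after permanent discontinuation of study drug", and then "Patients will subsequently be monitored for vital status in the Observation Period of this protocol". It names patients who stop for toxicity only to say that their tumour assessments go on.
- Flow chart: FUP is timed from discontinuation of study drug alone, and the Observation Period is timed from FUP.
- Section 6.2.3: the end of trial requires that all randomised patients have completed the FUP visit.

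Under Protocol Version 3.0, vital-status collection stops for all patients, once local approvals are in place where needed.

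**The concern.** A site that looks up what to do when a patient stops drug will go to Section 3.3.4.1.1, which is the specific rule. Followed as written, it omits the FUP visit for the group whose stopping is itself a tolerability measure: Section 5.2.1 assesses tolerability by dose reduction and by discontinuation due to adverse events. Where the protocol states the purpose of the 28-day visit, for patients whom the sponsor removes from treatment, it says "an end of treatment and a follow up visit 28 days later will be performed to ensure all adverse events are followed up".

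The safety window does not shrink to match. Section 5.2.2.2 requires reporting of all adverse events to 28 days after the last dose. Protocol Section 7.3.3 and SAP Section 7.8.1 analyse events over the same window. The data would be due without the visit scheduled to collect them.

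The excepted group is also poorly defined. Reason 5 covers adverse events of any cause, and disallowed dose reductions, but Section 3.3.4.1.1 describes it as study drug toxicity. ILD, also an adverse event, is reason 4 and does get the visit. Because the two arms have different dose-reduction steps, the size of the reason-5 group could differ by arm. The documents give no rate for either arm.

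**Working it through.** The plan states no figure that is in dispute. The check is a comparison of texts, followed by a bound on the days affected.

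**1. The rules side by side**

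| Place in protocol | FUP visit | Vital status | Exception for reason 5 |
|---|---|---|---|
| 3.3.4.1.1, first sentence | Required | Required, after FUP | Yes |
| 3.3.4.1.1, second sentence | Not mentioned | Pointer to flow chart, patients not stated | None for tumour assessments (only reasons 2 and 3 are left out) |
| 3.1 | Required after permanent discontinuation | Required afterwards | None |
| Flow chart | 28 to 35 days after discontinuation | Every 28 days after FUP | None |
| 6.2.3, end of trial | Required in all randomised patients | Not mentioned | None |

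The first row conflicts with the third and fourth on both steps, and with the fifth on FUP.

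**2. Does the second sentence of 3.3.4.1.1 repair the first?** For vital status, possibly: the pointer to the flow chart can be read as covering the patients just mentioned, who include reason 5. For FUP, no: the visit is not mentioned. Even the repair of vital status is incomplete, because the flow chart counts the Observation Period from FUP, and a patient without FUP has no starting point.

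**3. Who is left out, reason by reason.** Reasons 1, 2, 3 and 4 are sent to FUP. Reason 5 is not. It is the only listed reason without the visit.

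**4. Days without a later scheduled safety visit.** Inputs:

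- Adverse event window: 28 days after the last dose (Protocol 5.2.2.2 and 7.3.3; SAP 7.8.1).
- End-of-treatment (EOT) visit: *e* = 0 to 7 days after permanent discontinuation (flow chart).
- Interruption between last dose and permanent discontinuation: *g* days. It is 0 if discontinuation is dated from the last dose; 14 if it follows the full pause in the dose-reduction tables (4.1.4.1.2 and 4.1.4.2.1); and up to 28 for unrelated events (text after the afatinib table in 4.1.4.1.2).

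Days of the window after EOT = max(0, 28 − (*g* + *e*)):

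| *g* | EOT, days after last dose | Days remaining |
|---|---|---|
| 0 | 0 to 7 | 28 − 7 = 21 to 28 − 0 = 28 |
| 14 | 14 to 21 | 28 − 21 = 7 to 28 − 14 = 14 |
| 28 | 28 to 35 | 0 |

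The range over all cases is 0 to 28 days.

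**5. What FUP contains.** The flow chart marks five procedures for it: clinical assessment, vital signs, performance status, safety laboratory tests and questionnaires. Version 3.0 ends the questionnaires, leaving 5 − 1 = 4. The adverse event row is a span whose columns cannot be read reliably in this copy, so it is not counted.

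**The case against.** The strongest reply is that this is an omission, not an instruction. Section 3.3.4.1.1 never says that reason-5 patients skip FUP, and several unqualified statements elsewhere say that patients have it. The sentence in Section 3.3.4.1 about a follow-up visit for patients removed from treatment could be read broadly as well, although its paragraph concerns removal by the sponsor. Most sites would probably follow the flow chart. That is a fair argument about likely practice. But the text makes an explicit exception, and nothing in the documents says that the general rule prevails over the specific one.

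Second, the participation diagram in Section 3.1 is not shown, and it carries a footnote for patients who stop because of an adverse event. It may show a separate path, perhaps one in which tumour assessments precede the Observation Period, and so explain the exception. This stands as a limit: the point is confined to the text, and the diagram must be checked before the wording is changed. If the diagram does show a separate path, Section 3.3.4.1.1 must still agree with Sections 3.1 and 6.2.3.

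Third, adverse event reporting is a duty that does not depend on the visit. This stands. A reader might infer that late adverse events would go unrecorded; the documents do not support that. What is lost is a scheduled examination and laboratory check. Tumour-assessment contacts also continue.

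Fourth, a reader might infer that survival data were lost for patients who stopped for toxicity, biasing overall survival. The documents do not support that either. The run-on clause may keep these patients under vital-status follow-up, and deaths could also come to light through continued tumour assessment. Version 3.0 ends vital-status collection and, by its own rationale, follows the database lock for the primary survival analysis. The protocol text in force before that is not available here. Nor can such a loss be sized by subtracting the 632 planned deaths from the 795 patients entered: the remainder includes everyone still alive, whatever their reason for stopping.

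**Conclusion.** Section 3.3.4.1.1 is wrong as written. Its first sentence excepts reason-5 patients from FUP and the Observation Period, against Section 3.1 and the flow chart on both steps and Section 6.2.3 on FUP. The vital-status half may be cured by the run-on clause; the FUP half is not cured within that section. It is probably a drafting slip, but it concerns who receives the last scheduled safety visit, so it should be corrected.

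The size is modest. For a patient handled literally, four or five scheduled procedures are missed, and between 0 and 28 days of the 28-day adverse event window have no later scheduled safety visit. That range rests on EOT at 0 to 7 days and on interruptions of 0 to 28 days before permanent discontinuation. No figure for the number of patients affected can be given, and no actual loss is shown. Under Version 3.0 the FUP conflict still applies to anyone remaining on drug. The survival concern is secondary and historical.

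The point concerns reason 5 only. It should not be read as covering everyone who stops for an adverse event, since ILD is listed separately and does lead to FUP.

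**What to change.** Reconcile Section 3.3.4.1.1 with Section 3.1, the flow chart and Section 6.2.3, so that the FUP visit, and vital status for as long as it is collected, apply whatever the reason for stopping drug. Keep the existing exception in Section 3.3.4.1.1 for patients who withdraw consent to further procedures and follow-up.

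One way is to remove the reason-5 exception from the first sentence, and to end the second sentence before its Observation Period clause so that the clause stands alone. Before doing so, check that the participation diagram in Section 3.1 gives the same pathway, and correct it if it does not.

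The cost is one corrected passage and a check of one diagram. No new visit is created: FUP is already planned for the other stopping reasons and, under Section 3.1 and the flow chart, for these patients too. The change touches no dose or stopping rule.
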